6.2.1 Scientific Rationale for Study Design

[figure not shown]
Complete details of the study design are provided in Section 8.1.

Participants having a confirmed diagnosis of NASH and compensated cirrhosis will be enrolled in this multicenter, double-blind, placebo-controlled, randomized, parallel-group study to demonstrate the efficacy and safety of BMS-986036.

NASH patients with compensated cirrhosis have a high unmet medical need for approved therapies and compared to NASH patients with earlier stages of fibrosis, they are more likely to have a favorable benefit/risk profile for treatment with BMS-986036. Compared to NASH patients with stage 1-3 fibrosis, NASH patients with compensated cirrhosis have worsened clinical outcomes and disease-specific mortality.^{22,23,24} Moreover, the risk of liver-related mortality increases exponentially with each increase in fibrosis stage.²⁵ Demonstration of an improvement in fibrosis should be highly predictive of clinical benefit.

NASH grade will be assessed by liver biopsy histology. Fibrosis stage will be assessed by liver histology as well as a number of noninvasive measures. In addition, PRO-C3 levels in participants will be measured during the course of the study in order to collect more data on its potential as a pharmacodynamic (PD) biomarker of fibrosis. The correlation of baseline PRO-C3 levels with response to BMS-986036 will also be assessed. Markers of liver injury, metabolic improvements, and other liver-related outcomes will also be examined. Safety, including hematology and blood chemistry results, electrocardiograms (ECGs), and other potential safety issues (e.g., gastrointestinal AEs, immunogenicity, injection reactions, and effects on bone), will be monitored throughout the study.

PK profiling of BMS-986036 will be performed on all participants based upon trough sampling prior to dosing at each visit.

The primary efficacy endpoint of the study will be based on the independent histological evaluation of liver biopsy at 48 weeks – a timepoint at which meaningful clinical benefits in fibrosis and NASH disease activity are expected in the selected patient population treated with BMS-986036.

The design and dose selection of future Phase 3 studies with BMS-986036 will be based upon the totality of the efficacy, safety and PK analyses from this study and from MB130-068, a Phase 2 study of BMS-986036 in participants with NASH and stage 3 liver fibrosis.

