8.5.1.1 Liver Biopsy

A liver biopsy will be performed at Screening if no liver biopsy specimen collected within 6 months (26 weeks) prior to informed consent is available and readable by the Central Pathologist.

The on-treatment liver biopsy should be performed within \pm 7 days of the Week 48 Visit. However, if a biopsy cannot be scheduled within the window specified above, the biopsy should be performed as close to schedule as possible.

For participants prematurely discontinuing study medication, liver biopsy will be performed at the ET Visit if the participant has completed at least Week 20. If a participant discontinues study participation prior to Week 20 they should consider having a liver biopsy at ET.

Histological assessment of the tissue sample will be conducted by a blinded Central Pathologist. The central reader will be a medical doctor, board certified in pathology, with experience in liver pathology in a clinical study setting.

The on-treatment liver biopsy results will remain blinded to site personnel until after the study database is locked; incidental findings of potential clinical relevance (as determined by the medical monitor) from the central pathologist will be provided to the investigator.

Any incidental findings of potential clinical relevance that are not directly associated with the objectives of the study should be evaluated and handled by the investigator per the site's standard of care and clinical judgment.

Liver tissue should be collected using a 16 gauge (or larger) cutting needle (e.g., Bard, Microvasive, or TruCut) whenever possible. Use of suction needles (e.g., Menghini, Jamshedi, or Klatskin) are allowed, but may cause fragmentation of fibrotic specimens and impede the evaluation of fibrosis, and should therefore be avoided, if possible. At least 2 cm length of tissue should be obtained.

Additional details on the acquisition, quality requirements, histological preparation, and shipping of histological samples are in the Central Laboratory Manual and the Central Pathology Manual.

Histological Scoring

NASH CRN

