9.5.2.1 Primary Endpoint

The primary endpoint is the proportion of participants who achieve a ≥ 1 -stage improvement in fibrosis (as defined by NASH CRN Fibrosis Score) without worsening of NASH (as defined by the NAFLD Activity Score) at Week 48, as determined by liver biopsy.

For this protocol, improvement in fibrosis is defined as a decrease of fibrosis by ≥ 1 point, as determined by the NASH CRN Fibrosis Score. Worsening of NASH is defined as an increase of the NAFLD Activity Score (NAS) by ≥ 1 point (see Section 8.5.1.1).

A Cochran-Armitage trend test with a one-sided 0.05 level of significance will be used to examine the linear trend among the proportions across treatment groups. Also, 95% confidence intervals for the odds-ratio of each BMS treatment group to placebo will be provided.

A sensitivity analysis using an extended Cochran Mantel-Haenszel (CMH) correlation test³⁷ will be used to assess the trend among the proportions for treatment groups with an adjustment to strata. A two-sided 0.10 level of significance will be used.

Since this is a Phase 2 study, no adjustment for multiplicity will be applied.

All participants who prematurely discontinue from treatment without a biopsy at Week 48 (or ET, if applicable) or otherwise have a missing Week 48 (or ET, if applicable) biopsy result will be considered nonresponders for the primary analysis of the primary efficacy endpoint. In addition, a completer analysis of the primary endpoint will be performed excluding participants without a Week 48 biopsy.

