9.5.2.3 Methods for Handling Treatment Discontinuations and Other Causes of Missing Data

Participants who prematurely discontinue study medication will be expected to complete an Early Termination visit (Week 48/ET) and must continue to be followed for follow-up visits/procedures per the Schedule of Activities (e.g., Week 52/PTFU; Section 1).

Primary efficacy analyses will include all data that are collected on a participant during the study even after treatment discontinuation. All primary efficacy analyses will be performed with the mITT population, analyzed according to randomized treatment.

Additional details for handling of missing data will be provided in the SAP.

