## 6.4 Exploratory Analyses

Analyses for exploratory endpoints (including biomarkers) will be performed using the mITT or safety populations. Categorical and continuous data will be summarized descriptively as presented in SAP [Section 6.5](#).

Exploratory dichotomous response variables will be summarized in a manner similar to that used for the primary and secondary efficacy analyses:

- Assessment of NASH CRN Fibrosis Score at Week 48
  - Proportion of participants with  $\geq 1$  stage improvement
  - Proportion of participants with  $\geq 2$  stage improvement
  - Proportion of participants with  $\geq 2$  stage improvement without worsening of NASH
  - Proportion of participants with NASH resolution
  - Proportion of participants with NASH improvement
- Assessment of Ishak Fibrosis Score at Week 48
  - Proportion of participants with  $\geq 1$  stage improvement
  - Proportion of participants with  $\geq 2$  stage improvement
- Assessment of CPA at Week 48
  - Proportion of participants with any improvement
- Hepatic fat fraction as measured using MRI-PDFF at Week 24 and Week 48
  - Proportion of subjects with  $\geq 30\%$  relative reduction,  $\geq 20\%$  relative reduction,  $\geq 10\%$  relative reduction, and  $\geq 5\%$  absolute reduction
- Liver stiffness as determined by MRE at Week 24 and Week 48
  - Proportion of subjects with  $\geq 19\%$  reduction
  - Proportion of subjects with  $\geq 15\%$  reduction
- Fibroscan elastography results at Week 48
  - Proportion of subjects with any improvement

In addition, summaries of  $\geq 1$  stage improvement, no change, and worsening will be tabulated and graphically presented for NASH CRN Fibrosis Score, Ishak Fibrosis Score, and NAS Total at Week 48. Participants without a Week 48 (or ET result) will be classified into the "Worse" category for these exploratory summaries.

Similarly to the primary and secondary efficacy endpoints, for exploratory endpoints based off the liver biopsy, the Week 48 result or ET biopsy will be used for Week 48 derivations. Participants without a Week 48 or ET biopsy will be classified as non-responders for liver biopsy endpoints at Week 48. Early termination visits for non-biopsy endpoints such as imaging and biomarkers may occur at other time points and will not

Sponsor: Bristol-Myers Squibb

Protocol No.: MB130-069

be summarized together with Week 48. For non-biopsy endpoints, ET will be summarized separately in the summary tables.

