#### 7.1 Week 52 Analysis

The Week 52 data analysis is based on all subjects who have completed the Week 52/PTFU visit. A data cut-off date of 08Oct2020 is applied to the raw data extract for the locked database. The study will continue to collect data for the long-term follow-up. in a blinded fashion.

- All Efficacy data will be summarized based on mITT principle for DB Lock defined by eCRF date cut-off 08Oct2020 on all participants who have completed liver biopsy.
- If the biopsies were delayed (due to impact of COVID-19 or other causes) and performed between Week 48 and Week 52, the biopsies results will be included in the planned Week 48 visit.
- Safety data will be summarized using Safety population through DB lock defined by eCRF date cut-off date of 08Oct2020.
- All available data beyond Week 52 will be summarized descriptively.

Sponsor and designee personnel may be unblinded once all participants have completed the Week 52/PTFU visit and all data have been collected through that time point to facilitate analyses. The list of TFLs to be provided for this analysis will be kept in a separate document outside the SAP.

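### The plan gives two answers for a completer's liver biopsy taken after Week 52, and sets no minimum week for an early-termination biopsy to count as the Week 48 result

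*SAP*

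**What the plan says.** **Target time.** The primary endpoint is histological response at Week 48. Protocol 6.2.1 justifies that choice as "a timepoint at which meaningful clinical benefits in fibrosis and NASH disease activity are expected".

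**Late biopsies.** Protocol 8.5.1.1 gives a window of 7 days either side of the Week 48 visit and adds that "if a biopsy cannot be scheduled within the window specified above, the biopsy should be performed as close to schedule as possible". It sets no latest date. SAP 7.1 covers biopsies delayed by COVID-19 or other causes: those "performed between Week 48 and Week 52, the biopsies results will be included in the planned Week 48 visit". The same list ends with "All available data beyond Week 52 will be summarized descriptively", and SAP 7.2 reports data collected after the Week 52/PTFU visit in a separate analysis. SAP 8.3 keeps an assessment made outside its window at the planned visit under which it was recorded. Protocol 9.5.2.3 states: "Primary efficacy analyses will include all data that are collected on a participant during the study even after treatment discontinuation".

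**ET biopsies.** Protocol 8.5.1.1 calls for a biopsy at the ET visit once Week 20 has been completed. Before that it is optional: "If a participant discontinues study participation prior to Week 20 they should consider having a liver biopsy at ET". SAP 6.4, describing a rule shared with the primary and secondary endpoints, says that "the Week 48 result or ET biopsy will be used for Week 48 derivations".

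**Missing biopsies.** Under protocol 9.5.2.1 and SAP 6.1.1, a participant with no Week 48 biopsy, or ET biopsy where applicable, is a non-responder in the primary analysis.

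**The concern.** The endpoint is binary and a missing result counts as failure, so the definition of a Week 48 biopsy decides who is a responder. That definition is open at both ends.

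At the late end, a participant who took all 48 doses and was biopsied in Week 53 with a one-stage improvement is a responder under SAP 8.3 and protocol 9.5.2.3. On one natural reading of SAP 7.1 with 6.1.1, the same person is a non-responder. Two programmers could code that person differently and each cite the SAP.

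At the early end, a participant who stopped at Week 8 and accepted an optional biopsy contributes a Week 48 result, although the protocol's case for Week 48 rests on treatment duration. Because those biopsies are optional, who supplies one is partly self-selected.

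If late completers are lost equally across arms, response rates shrink and power falls. If late or early biopsies are distributed differently by arm, the dose trend itself is biased.

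**Working it through.** **1. The passages side by side**

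| Case | Pointing to use of the result | Pointing to non-response |
|---|---|---|
| Completer, biopsy between Week 48 and Week 52 | SAP 7.1 (explicit) | none |
| Completer, biopsy after Week 52 | SAP 8.3; protocol 9.5.2.3 | SAP 7.1 (stops at Week 52; later data descriptive) and 7.2, combined with 6.1.1 |
| ET biopsy, Week 20 completed | SAP 6.1.1, 6.4; protocol 9.5.2.1 | none |
| ET biopsy before Week 20 (optional) | same; no minimum week stated | none |

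Row 2 is the conflict. Row 4 has no lower limit: Week 20 governs whether a biopsy is called for, not whether its result counts.

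**2. Reproducing the protocol's power**

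Inputs from protocol 9.1: response rates p = 15%, 20%, 30%, 40%; 25 per arm; stated power at least 70%. From protocol 9.5.2.1: "A Cochran-Armitage trend test with a one-sided 0.05 level of significance will be used". The documents give no trend scores, so I assume s = 0, 1, 2, 3 (mean 1.5).

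- U = n × Σ p(s − 1.5) = 25 × (−0.225 − 0.100 + 0.150 + 0.600) = 25 × 0.425 = 10.625
- Null SD = √[p̄(1 − p̄) × n × 5] = √(0.2625 × 0.7375 × 125) = 4.919
- Alternative SD = √[n × Σ p(1 − p)(s − 1.5)²] = √(25 × 0.9194) = 4.794
- Power = Φ[(10.625 − 1.645 × 4.919) / 4.794] = Φ(0.528) = 0.701

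Simulation gives 0.709. The stated figure reproduces.

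**3. Power at the final size, 38 per arm (protocol 6.2)**

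U = 38 × 0.425 = 16.15, null SD 6.065, alternative SD 5.911, so power = Φ(1.045) = 0.852 (simulated 0.857).

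**4. Equal loss across arms**

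Let a share m of every arm, unrelated to true response, be scored non-response for lateness. Each rate becomes p(1 − m). The documents give no value of m; these are assumptions.

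| m | Rates, % | Formula | Simulated |
|---|---|---|---|
| 0 | 15 / 20 / 30 / 40 | 0.852 | 0.857 |
| 5% | 14.25 / 19 / 28.5 / 38 | 0.829 | 0.834 |
| 10% | 13.5 / 18 / 27 / 36 | 0.804 | 0.809 |
| 20% | 12 / 16 / 24 / 32 | 0.747 | 0.753 |

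At m = 10% the top-dose difference from placebo falls from 25 to 22.5 points.

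**5. Unequal loss, 38 per arm**

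- All true rates 15%, loss graded in equal steps from 0% at 40 mg to 10% or 20% at placebo: simulated one-sided type I error is 7.8% or 11.2%, against 5.3% with no loss.
- Planning rates, loss graded the other way, from 0% at placebo to 10% or 20% at 40 mg: power falls to about 0.75 or 0.61.

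**6. Single participants and time off drug**

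One reclassified participant moves an arm's rate by 1/38 = 2.6 points, whether the biopsy is late or early. With 48 weekly doses the last falls on Day 1 + 47 × 7 = Day 330. Week 52 is Day 1 + 52 × 7 = Day 365. SAP 7.1 therefore already accepts biopsies up to about 365 − 330 = 35 days after the last dose.

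**The case against.** The strongest reply is that SAP 7.1 only includes and excludes nothing. It says where a biopsy between Week 48 and Week 52 goes; it does not say that a later one is dropped. The sentence on data beyond Week 52 may concern the follow-up scans, antibodies and biomarkers, and a biopsy obtained late is not plainly missing. SAP 8.3 and protocol 9.5.2.3 would then fill the gap. This stands in part. A reader might infer that the plan contains a firm Week 52 cap under which later biopsies are non-responses. No sentence says so; that reading has to be assembled from SAP 7.1, 7.2 and 6.1.1. What remains is an ambiguity on the primary endpoint, in the one passage written for delayed biopsies.

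Second, using ET biopsies is a prespecified choice in both documents, and protocol 9.5.2.3 supports keeping them. That also stands: scoring an observed early result as non-response in the primary analysis would run against that section. A reader might also infer that responses on very early ET biopsies are mostly sampling variation. The documents do not support this. Protocol 8.5.1.1 says that pathologists' staging of fibrosis varies considerably. It does not mention sampling, and reading variation applies at Week 48 too.

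Third, protocol 9.5.2.1 plans a completer analysis excluding participants without a Week 48 biopsy. It helps little, because the SAP's primary-analysis sections do not define it and it does not settle which late or ET biopsies are Week 48 biopsies. The sensitivity analyses in SAP 6.1.1.1 vary the model, not the biopsy timing. The COVID-19 summaries in SAP 6.5.7 count visits.

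Finally, the loss shares are hypothetical, and equal loss costs power without inflating type I error. Both points are correct.

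**Conclusion.** The concern holds as a conflict and a gap, not as a stated rule. A completer's biopsy after Week 52 can be scored two ways under the current text, and an ET biopsy from any week can supply the Week 48 response without any analysis showing how much that matters.

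The size depends on counts that the documents do not give. If the restrictive reading were programmed and 5% to 20% of each arm were affected equally, simulated power would fall from about 0.86 to between 0.83 and 0.75. These figures rest on the protocol's planning rates, equally spaced scores, 38 per arm, and lateness unrelated to response. If nobody is biopsied after Week 52, the late-end question costs nothing. Unequal loss is the more serious case because it moves the trend in either direction, but nothing in the documents shows that loss would differ by arm. The point should be settled before unblinding, because afterwards a choice between the two readings could be influenced by the results.

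**What to change.** Before unblinding, amend SAP 7.1, with a matching sentence in 6.1.1:

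1. **Late biopsies.** For participants who completed treatment, use a delayed biopsy obtained by the data cut-off, on its own reading, as the Week 48 result. This aligns 7.1 with SAP 8.3 and protocol 9.5.2.3. Add a sensitivity analysis scoring biopsies after Week 52 as non-response.
2. **ET biopsies.** Keep them in the primary analysis, as both documents specify, and state that no minimum week applies. Add a sensitivity analysis scoring ET biopsies taken before the Week 48 window as non-response, and a separate one doing so only for those before Week 20.
3. **Reporting.** Tabulate study day of biopsy by arm, so that any imbalance in timing is visible.

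The cost is SAP wording, three reruns of an existing program and one table. No study procedure changes. The downside is that some late biopsies will be further off drug than the roughly 35 days already accepted at Week 52; the first sensitivity analysis shows whether that affects the conclusion.

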#### 7.2 Long-term Follow-up Analysis

Data collected after the Week 52/PTFU visit (or early termination) will be reported in a separate analysis once all participants have completed long term follow-up. The list of TFLs to be provided for this analysis will be kept in a separate document outside the SAP.

Sponsor: Bristol-Myers Squibb

Protocol No.: MB130-069

### 7.3 Exploratory Analyses

Any exploratory analyses completed to support study analyses in the Clinical Study Report (CSR), which were not identified in the statistical analysis plan, will be documented as such in the CSR.

## 8.0 Conventions and General Definitions

### 8.1 General Definitions

Term	Definition
Study Day	Study day is calculated as: assessment date – date of first dose + 1
Baseline	Unless otherwise stated, Baseline is defined as the last measurement prior to dosing on Day 1 (Week 0). If the measurement on Day 1 is missing or not available, then a prior measurement during the screening period may be used as baseline.
Change from Baseline	Change from baseline is defined as (value at post-baseline visit – value at baseline).
Change in the maximum post-baseline value	Change from baseline in the maximum post-baseline value is defined as highest observed value post-baseline. The change is calculated using this value as the post-baseline value.
Percent Change from Baseline	Percent change from baseline is defined as $([\text{value at post-baseline visit} - \text{value at baseline}]/\text{value at baseline}) \times 100$ . If the baseline value is 0 and the post-baseline value is also 0, then the percent change from baseline is set to 0. Percent change from baseline is not calculated if the baseline value is zero or baseline or post-baseline value is missing.
Study Treatment	For the purposes of the calculations included in this SAP, study treatment will include only doses of BMS-986036 (dose levels of 10 mg QW, 20 mg QW or 40 mg QW) or placebo QW.
Duration of Study Treatment (weeks)	Duration of study treatment in weeks will be defined as: (date of last dose of study treatment – date of first dose of study treatment + 7) / 7.
Treatment Completion (%)	Treatment completion (%) will be calculated as the total number of weeks of treatment received divided by the total number of expected doses (48), multiplied by 100.
End of Study (EOS) Date	The EOS date is the date recorded on the eCRF that a participant either discontinued or completed the study. If the participant is lost

Sponsor: Bristol-Myers Squibb

Protocol No.: MB130-069

	to follow-up, the EOS date will be the date of the last visit assessment obtained.
First Dose Date – Study	The date a participant received their first dose as recorded in the eCRF as date study treatment was administered.
Last Dose Date – Study	The date of last recorded dose on the eCRF for a subject.
Unscheduled assessments	Unscheduled measurements will be included in the listings. With the exception of unscheduled measurements used for baseline and as specified in section 8.12 , unscheduled measurements will be excluded from the descriptive statistics and statistical analysis.
Prior, Concomitant, and Follow-up Medications	Prior medications are defined as medications taken prior to the first dose of study treatment and discontinued prior to the first dose of study treatment. Concomitant medications are defined as any medication started before/on/after the first dose of study medication until the Week 52/PTFU Visit. Follow-up medications are defined as any medication taken after Week 52/PTFU Visit until the 6 Month Post PTFU Visit that could potentially impact bone mineral density assessments. Any Concomitant medications continued Post Week 52/PTFU will also be considered as Follow-up medication.

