8.5.4 Laboratory Assessments

Participants should not administer study medication on the days of clinic visits until after all laboratory samples have been collected (see [Table 8](#) below). Blood samples will be collected according to the schedule in Section 1. In addition, a number of hematology and blood chemistry values collected as part of the safety laboratory assessments will also be used to determine FIB4 index, APRI, and NAFLD Fibrosis Scores according to the schedule in Section 1.

Safety (hematology, blood chemistry, and urinalysis), efficacy, and exploratory laboratory assessments to be conducted during the study are listed in Table 8 below. The schedule for collection of samples for each assessment is in Section 1. Laboratory assessments will be conducted by central or specialty laboratories. Additional details on the collection, processing, and submission of samples for laboratory assessments are in the Study Laboratory Manual. If clinically indicated, repeat laboratory testing may be performed at a local lab.

Investigators must document their review of each laboratory safety report. A central laboratory will perform the safety analyses and will provide reference ranges for these tests. Results of clinical laboratory tests performed during Screening must be available prior to dosing.

In addition to those detailed assessments outlined in Table 8 below, serum, plasma and urine may be assayed for exploratory markers associated with liver, fibrosis, [REDACTED] or metabolic syndrome disease including markers associated with the BMS-986036 target pathway or with organs or pathways impacted by FGF21.

Urine or serum samples will be collected for pregnancy testing for WOCBPs. A negative serum pregnancy test is required during Screening. After the Screening Period, urine pregnancy testing will be conducted instead of serum testing at any site where it is allowed by the IRB/EC committee overseeing study conduct at that site. Women who are considered postmenopausal will have follicle-stimulating hormone testing performed during Screening.

Urine samples to test for drugs of abuse will be collected during Screening.

Repeat assessments for any laboratory assessment will be permitted according to the investigator's clinical judgment.

Table 8 Laboratory Assessments

ELF Assay (to be collected at Day 1, Week 24, and Week 48/ET). Participants will fast for 8 hours prior to collection of blood samples for these assessments:
--

- Hyaluronic acid

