- Procollagen 3 amino terminal peptide
- Tissue inhibitor of metalloproteinases 1 (TIMP-1)

Laboratory Metabolic Markers (to be collected at Screening, Day 1, Week 24, and Week 48/ET).

Participants will fast for 8 hours prior to collection of blood samples for these assessments:

- Low-density lipoprotein cholesterol
- High-density lipoprotein cholesterol
- Triglycerides
- Plasma glucose – *Also used for NAFLD Fibrosis Score*
- Plasma insulin
- Hemoglobin A1c – *also to be collected at Long-Term Immunogenicity Follow-Up Visits as applicable (see Section 8.5.3.6)*

Hepatitis Assessments (to be collected at Screening only- see [Appendix 3](#) for diagnosis and exclusion criteria):

- Hepatitis B core antigen antibody
- Hepatitis B surface antigen antibody
- Hepatitis B surface antigen
- Hepatitis B virus DNA
- Hepatitis C virus antibody
- Hepatitis C virus RNA

Pregnancy Testing (to be collected at each visit through the Week 52/PTFU Visit):

- Serum or urine β -HCG. Women of childbearing potential only. Serum β -HCG to be collected at Screening and serum or urine β -HCG to be collected thereafter according to local laws and regulations and Institutional Review Board/Ethics Committee requirements)
- Follicle-stimulating hormone (Screening only for postmenopausal women)

Hematology (to be collected at each visit through the Week 52/PTFU Visit):

- Complete Blood Count
 - White blood cells, including differential
 - Red blood cells
 - Hemoglobin
 - Hematocrit
 - Platelet count – *Also used for FIB4, APRI, and NAFLD Fibrosis Score*
 - Mean corpuscular hemoglobin (MCH)
 - Mean corpuscular hemoglobin concentration (MCHC)
 - Red cell distribution width (RDW)
- Prothrombin time
- Partial thromboplastin time
- International normalized ratio – *Also used in MELD and Child-Pugh Turcotte scoring*

Blood Chemistry (to be collected at each visit through Week 52/PTFU and at Long-Term

Immunogenicity Follow-Up Visits as applicable [see Section 8.5.3.6]):

- AST – *Used as both safety and efficacy endpoints. Also used for FIB4, APRI, and NAFLD Fibrosis Score*
- ALT – *Used as both safety, efficacy endpoints, and for FIB4, APRI, and NAFLD Fibrosis Score*
- Serum glucose
- Total bilirubin
- Indirect bilirubin
- Alkaline phosphatase
- Lactate dehydrogenase
- Creatinine
- Blood Urea Nitrogen
- Uric acid
- Total Protein
- Albumin – *Also used for NAFLD Fibrosis Score.*
- Sodium
- Potassium
- Chloride
- Carbon dioxide
- Calcium
- Phosphorus
- Glomerular filtration rate

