#### 4.3.5 Clinical Laboratory Parameters

- Absolute and change from baseline values
- Potential hepatotoxicity by time point
  - Aspartate aminotransferase (AST) or alanine aminotransferase (ALT) > 3 x upper limit of normal (ULN) or > 5 x ULN
  - Total Bilirubin > 2 x ULN
  - (AST or ALT) > 3 x ULN and Total Bilirubin > 2 x ULN
- Postbaseline abnormalities defined by the below categories:
  - Serum albumin < 2.8 g/dL
  - Platelet count < 75 x 10^3/ μL
  - Fasting plasma glucose < 60 mg/dL or > 350 mg/dL
  - Fasting triglycerides > 500 mg/dL
  - Estimated glomerular filtration rate (eGFR) < 30 mL/min/1.73 m^2

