### **6.2.4 Clinical Laboratory Parameters**

Based on the safety population, continuous laboratory results will be summarized by visit, treatment group, and pooled BMS-986036 (in both SI units and US Conventional units). Categorical results such as those for urinalysis will be summarized by number and percentage of participants in each category. These summaries will be based on central laboratory results, except in rare circumstances in which only a local lab value is available then a local lab value may be used. This value will be presented in the same unit and summarized with the central results from other participants. Summaries will present both actual and change-from-baseline results for continuous values.

Sponsor: Bristol-Myers Squibb

Protocol No.: MB130-069

Altered postbaseline values will be descriptively summarized by counts and percentages of participants ever experiencing specified altered values at any postbaseline time point.

Laboratory values below the lower limit or above the upper limit of quantification will be imputed to the lower or upper limit, respectively, for summary tables. The actual values will be displayed in the listings.

Box plots will be presented by time point. All laboratory data specified in the summary tables will be present in listings.

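### SAP 8.1 keeps unscheduled results out of descriptive summaries, so the SAP 6.2.4 count of participants ever having altered laboratory values may come out too low

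*SAP*

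**What the plan says.** SAP 8.1 (General Definitions, unscheduled assessments) sends unscheduled measurements to the listings. It states that, with two exceptions, "unscheduled measurements will be excluded from the descriptive statistics and statistical analysis". The exceptions are values used as baseline and whatever section 8.12 specifies. Section 8.12 is the validity rule for Fibroscan readings and mentions neither unscheduled nor laboratory data.

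SAP 6.2.4 plans this summary: "Altered postbaseline values will be descriptively summarized by counts and percentages of participants ever experiencing specified altered values at any postbaseline time point". The limits are in SAP 4.3.5. One list, headed "Postbaseline abnormalities defined by the below categories", covers serum albumin, platelets, fasting plasma glucose, fasting triglycerides and eGFR. A separate list, headed "Potential hepatotoxicity by time point", covers ALT or AST above 3 or 5 times ULN, total bilirubin above 2 times ULN, and the combination of ALT or AST above 3 times ULN with bilirubin above 2 times ULN.

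Protocol 8.5.4 says: "Repeat assessments for any laboratory assessment will be permitted", at the investigator's judgment. Protocol 8.5.3.1 also orders repeat liver tests within 48-72 hours of defined elevations, and laboratory checks two to three times a week for asymptomatic participants under close observation.

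**The concern.** An ever count is normally read as covering every post-baseline result. Applied as written, 8.1 removes any result coded as unscheduled, and 6.2.4 is not among its exceptions. If a participant's platelets first fall below the limit on a repeat between visits, a programmer following 8.1 leaves that participant out. A programmer following the plain sense of 6.2.4 counts the participant. The same SAP can therefore give two different safety tables, and the one that follows 8.1 can only be equal or lower.

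What is at stake is the descriptive laboratory safety summary in a population with compensated cirrhosis, where safety is a stated objective. No efficacy result depends on it.

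**Working it through.** The plan states no figure to reproduce. The check sets the rules side by side and asks which results can be lost.

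1. **The exceptions in 8.1.** Baseline values are irrelevant to a post-baseline count. Section 8.12 concerns Fibroscan only. If 8.13 was intended, it lets a missing component of FIB4, APRI, NAFLD Fibrosis Score or MELD be taken from a value within 3 days. Neither section returns an unscheduled laboratory value to the ever count.

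2. **The five altered-value rows.** Protocol Table 8 gives the schedule.
 - Fasting glucose and triglycerides: "Laboratory Metabolic Markers (to be collected at Screening, Day 1, Week 24, and Week 48/ET". Post-baseline draws are Weeks 24 and 48/ET, which is 2.
 - Albumin and eGFR: "Blood Chemistry (to be collected at each visit through Week 52/PTFU". Weeks 4, 8, 12, 16, 20, 24, 32, 40, 48 and 52 give 10. A conditional Month 14 chemistry draw (Protocol Table 3) can be added, though SAP 4.3 lists laboratory evaluations only through Week 52/PTFU.
 - Platelets: "Hematology (to be collected at each visit through the Week 52/PTFU Visit", which is also 10.

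 These are scheduled opportunities for a participant who completes the study. They follow from the protocol's design, not from 8.1, and do not measure loss. They show what the ever count rests on if unscheduled results are excluded.

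3. **The liver rows.** These are defined by time point, so excluding unscheduled values does not contradict them. The question is what can first appear on a repeat.
 - Normal-baseline trigger (ALT or AST above 3 times ULN): the 3 times row is already met at the trigger. The 5 times row, the bilirubin row or the combined row can first be met on the repeat.
 - Elevated-baseline trigger: it already requires bilirubin above 2 times ULN and ALT or AST above 200 U/L, so the bilirubin row is met. The ULN is not given. Since 200/5 = 40 and 200/3 = 66.7, the 5 times row is already met if the ULN is 40 U/L or less, and the combined row if it is 66.7 U/L or less. A repeat adds something only above those values.
 - Interruption rule, first scenario: its bilirubin criterion is relative to Baseline, not ULN, so bilirubin above 2 times ULN can first appear on the repeat liver profile it orders.

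4. **How repeats are coded.** Neither document says. A repeat recorded under a planned visit falls under SAP 8.3. That section keeps the value closest to the planned day, in the context of visit-structured tables.

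5. **Size of one reclassified participant.**
 - One arm of about 38: 1/38 = 2.6 percentage points.
 - Pooled active group: 3 × 38 = 114 to 155 × 3/4 ≈ 116, so 1/114 to 1/116, about 0.9 percentage points.

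**The case against.** The strongest reply is that the two sections can be reconciled. The SAP often uses time point for a planned assessment: 6.2.5 speaks of the baseline time point, 6.3.1 of scheduled time points, and the repeated-measures model in 6.4 reports time points from planned visits. On that reading 6.2.4 counts participants altered at any scheduled visit, and 8.1 fits. A reader might infer an outright contradiction, but the documents do not compel it. What stands is that 6.2.4 does not restrict itself in this way. Even on the narrow reading, the count omits crossings seen only on repeats.

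A reader might also infer that liver signals would vanish or that the liver rows conflict with 8.1. Neither follows. A scheduled trigger value is counted and every value is listed. Potential DILI is reported as an SAE whatever the visit coding, and treatment-emergent SAEs are tabulated (SAP 6.2.2). This cover is only partial. AE capture under Protocol 8.5.3.1 turns on clinical significance, seriousness, interruption or discontinuation, or corrective therapy, not on the 4.3.5 limits. The DILI definition in Protocol Appendix 9 excludes cholestasis and other apparent causes, including existing chronic liver disease.

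Two further points stand. The separate table shells, which are not available here, might settle the data basis. Protocol 8.5.1 also keeps data from non-protocol standard care out of the eCRF, so only repeats that the protocol permits or orders are at issue.

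**Conclusion.** The concern holds as a tension between a general exclusion and a specific count, with possible undercounting on the five altered-value rows. For the liver rows it is an omission: ALT or AST above 5 times ULN, or bilirubin above 2 times ULN, first seen on an unscheduled repeat can be missed.

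This rests on two assumptions: that at least some repeats are coded as unscheduled, and that some limit is first crossed on one of them. Protocol permission to repeat does not show how often either happens, so the total effect is unknown. A reader might infer a large undercount, but the documents give nothing to support a figure beyond the per-participant step shown above. It is worth fixing because it is cheap and removes a choice that would otherwise fall to the programmer.

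**What to change.** - In SAP 8.1, limit the exclusion of unscheduled measurements to by-visit summaries.
- In SAP 6.2.4, state that the ever counts use all post-baseline results in the database, scheduled and unscheduled. Keep the existing central-laboratory rule, under which a local value is used only when no central value is available.
- Apply the ever count on the same basis to the 4.3.5 hepatotoxicity categories, and keep the by-time-point rows.
- Check the 8.12 cross-reference; 8.13 looks like the intended target.
- Add a footnote giving the number of participants per arm with unscheduled tests.

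The cost is a few sentences in three sections, some programming and no new data from participants. SAP 1.0 already provides for logged changes before database lock. There are two limits. Participants tested more often have more chances to be counted; the footnote shows this but does not remove it. Liver repeats done locally enter only as far as the existing rule and the database contents allow. Bringing in every local result would override that rule and could need extra site data entry, so it is not proposed.
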